## **RESULTS**

### **Demographic Findings**

The distributions of gender and age of the groups were as follows: SP (seven male and four female subjects; mean age:  $40,9 \pm 9,28$  years); P (three male and eight female subjects; mean age:  $41 \pm 12,30$  years); SH (seven male and four female subjects; mean age:  $30,27 \pm 9,99$  years); H (three male and eight female subjects; mean age:  $26,36 \pm 4,20$  years).

The study groups were evaluated in terms of age and gender, and a significant difference was found between the groups in terms of mean age ( $\chi^2=16,567$ ; p=0.001). There was no

significant difference in terms of gender ( $\chi^2=0.364$ ;  $p=0.546$ ). The mean age of the H group was lower than the mean age of the patients in the SP ( $Z=18,000$ ;  $p=0.006$ ) and P groups ( $Z=16.682$ ;  $p=0.014$ ). It was determined that the mean age of the individuals was similar ( $Z=3,682$ ;  $p=1,000$ ) between group H and group SH.

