### **Statistical analysis**

SPSS for Windows Ver. for statistical analysis and graphics. 22.0 (SPSS Inc., Chicago, ILL, USA) and MS-Excel 2016 programs were used. Statistical significance level was accepted as p<0.05.

The normal distribution of the data in our study was evaluated with the Shapiro-Wilks test. The mean±standard deviation was used for the descriptive statistics for the normally distributed variables, and the median (min-max) value for the non-normally distributed variables. While examining the distribution of the gender variable in the groups, the result of the Chi-Square test was evaluated.

OneWay ANOVA test was applied to the variables showing normal distribution in the comparison of the data between groups. In post-hoc analyses, homogeneously distributed data according to Levene variance homogeneity test were evaluated with Tukey test, and data that were not homogeneously distributed were evaluated with Tamhane T2 test. Variables that did not show normal distribution were evaluated with the Kruskal-Wallis test. Bonferroni corrected Mann-Whitney U test was used in order to determine the group that caused the difference in the variables with a significant difference as a result of the Kruskal-Wallis test.

Paired-Sample T Test and Repeated Measured Analysis of Variance were used for the variables showing normal distribution in the evaluation of the within-group changes according to time. Significant differences as a result of analysis of variance were examined with Bonferroni, one of the multiple comparison tests. Variables that did not show normal distribution were analyzed with the Friedman test. The Wilcoxon test was used to determine the group that caused the difference in the variables with a significant difference as a result of the Friedman test.

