## **Biochemical Parameters**

### **GCF Periostin levels**

When the GCF Periostin data were examined, the difference between the groups was found to be statistically significant at the beginning ( $p=0.003$ ). In terms of periodontal disease, the amount of GCF Periostin in the P group was found to be significantly lower than in the H group ( $p=0.007$ ), while there was no statistically significant difference between the SP group and the SH group.

When evaluated in terms of smoking, it was observed that the GCF Periostin amount of the SP group was significantly higher than the P group ( $p=0.021$ ). There was no significant difference between the SH and H groups ( $p>0.05$ ).

A statistically significant difference was found between the groups on the 15th day ( $p<0.001$ ). When examined in terms of periodontal disease in the post-hoc analysis, it was found that the amount of GCF Periostin in the P group was significantly lower than in the H group, as at the beginning ( $p=0.002$ ). It was determined that there was no statistically significant difference between the SP group and the SH group. When evaluated in terms of smoking, it was observed that the GCF Periostin amount of the SP group was significantly higher than the P group ( $p=0.003$ ).

However, on the 30th day, it was determined that there was no statistically significant difference between the groups.

In the in-group evaluation of the change with treatment on a time basis, it was found that the GCF Periostin level in the SP group decreased over time ( $p<0.001$ ). In post-hoc analyzes, this decrease was observed to be significant between all times ( $p=0.009$ (0-15.days, respectively),  $p=0.001$ . (day 0-30) and  $p=0.003$ (day 15-30)). In the P group, there was no statistically significant difference in the evaluations of the 0th day, 15th day and 30th day within the group ( $p>0.05$ ).

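### The two smoking contrasts (SP-P and SH-H) are partly confounded with sex, and the planned group tests do not separate the two

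*Combined protocol and SAP*

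**What the plan says.** Demographic Findings lists four groups of 11: "SP (seven male and four female subjects; mean age", "P (three male and eight female subjects; mean age", "SH (seven male and four female subjects; mean age" and "H (three male and eight female subjects; mean age". It then reports no "significant difference in terms of gender", with chi-square 0.364 and p=0.546. The Statistical analysis section describes the purpose of that test: "While examining the distribution of the gender variable in the groups, the result of the Chi-Square test was evaluated".

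For the outcomes, the same section says "OneWay ANOVA test was applied to the variables showing normal distribution in the comparison of the data between groups", with Kruskal-Wallis and Bonferroni-corrected Mann-Whitney tests for non-normal variables. It names no covariate, and the document describes neither stratification nor matching by sex.

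The results sections read SP against P, and SH against H, as the comparisons on smoking. GCF Periostin levels has the one positive marker finding: "When evaluated in terms of smoking, it was observed that the GCF Periostin amount of the SP group was significantly higher than the P group". The p-values given for it are 0.021 at baseline and 0.003 on day 15. SH and H did not differ significantly on periostin at baseline. The smoking comparisons for the clinical indices, IL-17A and IL-17E are all reported as non-significant.

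**The concern.** The design crosses smoking with periodontal status. Sex is spread evenly over periodontal status but not over smoking. In both smoking comparisons a group that is about 64% male is set against one that is about 27% male, and nothing in the analysis allows for it. If a marker or a clinical index differs between men and women, part of that difference enters the smoking comparison. It can add to a positive result or offset a real difference and help produce a null one.

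The reported gender test appears to rule this out, so its value has to be checked. A correct four-group test would not settle the matter either, because it spreads an imbalance that lies on one axis over three degrees of freedom.

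**Working it through.** **Inputs.** From Demographic Findings, male/female: SP 7/4, P 3/8, SH 7/4, H 3/8. From GCF Periostin levels: SP-P p=0.021 (day 0) and p=0.003 (day 15). Assumed, not in the documents: a male-female difference of 0.25 to 1 SD in a marker.

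**1. The reported gender test.** The group counts sum to 20 men and 24 women. A goodness-of-fit test of 20:24 against 22:22 gives (20−22)²/22 + (24−22)²/22 = 8/22 = 0.364, 1 df, p=0.546. This is the reported figure exactly, so it tests the overall sex ratio and does not compare groups. The four-group test on the stated counts has expected counts of 5 men and 6 women per group and gives 4×(4/5) + 4×(4/6) = 5.867, 3 df, p=0.118.

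**2. Where the imbalance lies.**

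| Comparison | Male | Chi-square (1 df) | Pearson p | Fisher p |
|---|---|---|---|---|
| Smoking groups vs comparison groups, pooled | 14/22 vs 6/22 | 5.867 | 0.015 | 0.033 |
| SP vs P, or SH vs H, each alone | 7/11 vs 3/11 | 2.933 | 0.087 | 0.198 |
| Periodontitis vs health | 10/22 vs 10/22 | 0 | 1.0 | 1.0 |

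The whole four-group statistic (5.867) lies on the smoking axis.

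**3. Bias in an unadjusted contrast.** With no smoking effect and a male-female difference of d SD, the expected SP-P or SH-H difference is (7/11 − 3/11)×d = 0.364×d.

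- d=0.25: 0.09 SD
- d=0.5: 0.18 SD
- d=1: 0.36 SD

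In simulation (11 vs 11, no smoking effect), the nominal 5% t-test rejected in about 6%, 8%, 9% and 12% of trials at d=0.5, 0.8, 1.0 and 1.5.

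**4. Cost of adjustment.** Within SP and P, phi² = 2.933/22 = 0.133. The variance inflation is 1/(1−0.133) = 1.154, and the SE factor is √1.154 = 1.074.

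**5. Effect on the periostin result.** This is a two-sample t approximation with 11 per group. The SE in SD units is √(2/11) = 0.426, or 0.426×1.074 = 0.458 after adjustment (19 df).

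- Day 0: p=0.021 on 20 df means t=2.505, a difference of 2.505×0.426 = 1.07 SD.
- Day 15: p=0.003 means t=3.376, a difference of 1.44 SD.

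Removing the bias, if men have the higher values:

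| Assumed d | Day 0: t, p | Day 15: t, p |
|---|---|---|
| 0.25 | 2.13, 0.046 | 2.94, 0.008 |
| 0.5 | 1.94, 0.068 | 2.75, 0.013 |
| 1 | 1.54, 0.14 | 2.35, 0.030 |

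If women have the higher values, the bias runs the other way and adjustment enlarges the SP-P difference.

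**The case against.** Several objections carry weight.

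- **Confounding is partial.** Both sexes occur in every group and phi is √0.133 = 0.37. A reader might infer that smoking and sex cannot be told apart here; the counts do not support that.
- **The pooled p-value belongs to a comparison the document never makes.** The pairs it does compare give p=0.087 (Fisher 0.198). This stands as a caution about quoting 0.015 alone. The bias, however, depends on the 36-point gap and not on its significance.
- **The counts are in dispute.** The opening section states 22 men and 22 women; the groups sum to 20 and 24. Suppose two subjects listed as women were men. The pooled Pearson p would be 0.070 if both were in P or H, 0.016 with one on each side, and 0.003 if both were in SP or SH.
- **Sex is an unlikely full explanation of the periostin result.** It would need a male-female difference of about 1.07/0.364 = 2.9 SD on day 0 and 1.44/0.364 = 4.0 SD on day 15. SH-H has the same sex gap but no significant periostin difference at baseline, and the group differences are no longer significant by day 30 although the sex mix is fixed. A constant sex effect predicts neither, though with 11 per group this is only suggestive. A reader might infer that sex produced the finding; the documents do not show that.
- **Sex is not the only difference within SP-P.** SP is Grade C and P is Grade A, so a sex-adjusted SP-P contrast is still not a clean smoking comparison.

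What remains is that no analysis separates sex from these contrasts, and the one reassurance offered is a test of something else.

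**Conclusion.** The point holds as partial confounding. On the Demographic Findings counts, each smoking contrast compares 7/11 with 3/11 men and carries 0.364 times any sex difference in the outcome. For an assumed 0.25 to 1 SD sex difference this is 0.09 to 0.36 SD. The day-0 periostin result would stay just under 0.05 at 0.25 SD and lose significance at 0.5 to 1 SD (p about 0.07 to 0.14). The day-15 result would probably remain (p about 0.01 to 0.03). The null smoking comparisons are open to the same bias in either direction.

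This rests on the group counts being right, on P being non-smokers (its label gives only stage and grade, so this is inferred from how SP-P is used), and on treating the periostin p-values as two-sided t-tests without multiplicity correction. If they are already Bonferroni-corrected, the underlying differences are larger and harder to undo. The size and direction of any actual bias cannot be known from the documents.

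**What to change.** 1. Reconcile the 22/22 at enrolment with the 20/24 by group before any re-analysis.
2. In Demographic Findings, state that the smoking and comparison groups differ in sex, and replace the gender figure with a test that compares groups.
3. Report SP-P and SH-H adjusted for sex beside the unadjusted results: sex as a covariate (on ranks where the outcome is non-normal), or a van Elteren test stratified by sex. Label this as a sensitivity analysis, since it was not planned.
4. Qualify the smoking reading in the clinical, periostin, IL-17A and IL-17E sections if the adjusted estimate moves materially. Loss of significance alone, with 11 per group, is not a reason to withdraw it.
5. State that SP-P also differs in grade (C against A) and that sex adjustment leaves this in place.

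The cost is a re-analysis of data already held, one degree of freedom and about 7% wider intervals (variance inflation 1.15).

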### **Study Protocol and Statistical Analysis Plan**

Before the study, One Way ANOVA test with a significance level of 5% was used for the sample size calculation. Based on this analysis, the sample size was determined as at least 11 people in each group and a total of 44 subjects to detect a difference between groups. This cross-sectional study was approved by Ondokuz Mayıs University Clinical Research Ethics Committee (OMUKAEK) Samsun, Turkey (protocol number; 2019/324).

Fourty four individuals, 22 males and 22 females who were older than 18 were enrolled in the study. The study groups were selected according to the following criteria from individuals who applied to the Ondokuz Mayıs University Faculty of Dentistry Periodontology Department Clinic for treatment or control, accepted to participate in the study, were systemically healthy, did not take any medication in the previous 6 months, and did not receive periodontal treatment in the previous 6 months:

Group 1: (SP) Stage 3 Grade C patients (n:11)

Group 2: (P) Stage 3 Grade A patients (n:11)

Group 3: (SH) Periodontally healthy smokers (n:11)

Group 4: (H) Non-smokers with periodontally healthy (n:11)

Individuals were included as smokers if they had smoked  $\geq 10$  cigarettes/day for  $\geq 5$  years, whereas individuals were included as nonsmokers if they had no previous history of smoking. The periodontitis stage III patients were evaluated clinically and radiographically, and were selected to have teeth with CAL  $\geq 5$  mm in at least 30% of them. Exclusion criterias were as follows; patients under the age of 18, pregnant or lactating women, patients who have a history of with systemic disease or cancer or chemotherapy and radiotherapy or ongoing drug therapy who might be affect the clinical characteristics of periodontitis, patients who smoke less than 10 cigarettes/day or who quit smoking.

In order to standardize the study, all radiological and clinical examinations were performed by a single investigator. In clinical examination, Plaque Index (PI), Gingival Index (GI), bleeding on probing (BOP), probing depth (PD) and clinical attachment loss (CAL) scores were measured and recorded from 6 regions of each tooth (buccomesial, midbuccal,

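### The printed gender test (chi-square 0.364, p=0.546) is not a between-group test on the stated counts, which give 5.867 on 3 df, p=0.118, and those counts contradict the enrolled 22/22 split

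*Combined protocol and SAP*

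**What the plan says.** The Statistical analysis section names the test: "While examining the distribution of the gender variable in the groups, the result of the Chi-Square test was evaluated". Under Demographic Findings the split is given group by group, beginning "SP (seven male and four female subjects; mean age" and "P (three male and eight female subjects; mean age". SH repeats the SP split and H repeats the P split. The same section then says "The study groups were evaluated in terms of age and gender", and reports no "significant difference in terms of gender" with chi-square 0.364 and p=0.546. No degrees of freedom are given.

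The opening section (Study Protocol and Statistical Analysis Plan) describes the same sample differently: "Fourty four individuals, 22 males and 22 females who were older than 18 were enrolled in the study". It sets 11 people in each group, for example "Group 1: (SP) Stage 3 Grade C patients (n:11" and "Group 2: (P) Stage 3 Grade A patients (n:11".

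**The concern.** Two things do not fit.

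- **The statistic.** A test of sex across four groups has 3 df. A chi-square of 0.364 on 3 df would have a p-value far above 0.546, and splits as uneven as 7/4 against 3/8 should give a larger statistic.
- **The totals.** The group counts do not add up to 22 males and 22 females, although both statements account for all 44 people.

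The imbalance lies wholly between SP and SH on one side and P and H on the other. The contrasts SP vs P and SH vs H are the ones GCF Periostin levels reads as smoking effects, and SP vs P is significant there at day 0 (p=0.021) and day 15 (p=0.003). That SP is the smoker group is inferred from that wording. The Statistical analysis section describes no adjustment for sex. A reader who takes p=0.546 as evidence of good balance would dismiss sex as a possible confounder too readily.

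**Working it through.** **Inputs.** Males/females from Demographic Findings: SP 7/4, P 3/8, SH 7/4, H 3/8. Enrolled split from the opening section: 22/22. Group size: 11. Significance level from Statistical analysis: 0.05.

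**1. Totals.** Males 7+3+7+3 = 20; females 4+8+4+8 = 24; sum 44. Each group adds to 11, so dropout cannot explain the gap of 2 in each sex.

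**2. Trying to reproduce the printed figure.** The upper tail of 0.364 is 0.546 at 1 df, 0.834 at 2 df and 0.948 at 3 df, so the printed pair is a 1-df result. The 1-df between-group comparisons on the printed counts are:

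| Comparison | Chi-square | Continuity-corrected |
|---|---|---|
| SP-P, SP-H, P-SH, SH-H | 2.933 | 1.650 |
| SP-SH, P-H | 0 | 0 |
| SP+P vs SH+H | 0 | 0 |
| SP+H vs P+SH | 0 | 0 |
| SP+SH vs P+H | 5.867 | 4.492 |
| Any one group vs the rest | 1.956 | 1.100 |

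None is 0.364. Three other calculations do print as 0.364, p=0.546:

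- one-sample test of 20 vs 24 against 50:50: (20−22)²/22 + (24−22)²/22 = 0.3636, p=0.5465;
- a two-group table 12/10 vs 10/12 (22 males): 0.3636, p=0.5465;
- a continuity-corrected table 12/10 vs 9/13 (21 males): 0.3644, p=0.5461.

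The first uses the printed totals but says nothing about balance between groups. The other two need counts that differ from those printed.

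**3. The test as described.** Expected counts are 5 males and 6 females per group, and every observed count is 2 away from expected:

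chi-square = 4 × (2²/5) + 4 × (2²/6) = 3.200 + 2.667 = 5.867, 3 df, p=0.118.

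The exact p-value is 0.122, so the large-sample approximation is not the issue. Each smoking contrast alone (7/11 vs 3/11 male) gives Pearson p=0.087 and Fisher p=0.198.

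**4. If 22/22 is right.** Assume that exactly two people printed as female are male. With 5.5 of each sex expected per group and m the males in a group, chi-square = Σ(m−5.5)² × (2/5.5). There are ten possible tables:

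| Males SP/P/SH/H | Chi-square | p (3 df) | Exact p |
|---|---|---|---|
| 9/3/7/3, 7/3/9/3 | 9.818 | 0.020 | 0.025 |
| 8/3/8/3 | 9.091 | 0.028 | 0.035 |
| 8/4/7/3, 8/3/7/4, 7/4/8/3, 7/3/8/4 | 6.182 | 0.103 | 0.154 |
| 7/5/7/3, 7/3/7/5 | 4.000 | 0.261 | 0.315 |
| 7/4/7/4 | 3.273 | 0.351 | 0.481 |

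Three of the ten fall below 0.05. They are not equally likely, and larger offsetting miscounts cannot be excluded.

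**The case against.** The strongest reply is that this is a reporting slip with little effect. On the printed counts the non-significant conclusion survives, no analysis is chosen or adjusted by this test, and no biomarker result changes. All four sex splits are printed in the same section, so an attentive reader can see the imbalance. This stands, and it limits the seriousness of the point.

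A second reply is that the source is fairly clear. The one-sample test of 20 vs 24 is the only candidate built from printed figures, which would favour 20/24 and make the 22/22 sentence the slip. That is the likeliest reading, but it is not established. In six of the ten tables above, periodontitis against healthy gives 12/10 vs 10/12 or its mirror image, which prints identically. Those six include 9/3/7/3 and 7/3/9/3, both with p=0.020. The third table below 0.05, 8/3/8/3, does not give 0.364 on any simple 1-df comparison. Whichever source is right, the printed value is not a between-group test on the stated counts.

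A third reply is that confounding by sex is speculative. The documents show no sex effect on any biomarker, and SH vs H has the same split without a baseline periostin difference. SP and P also differ by periodontitis grade, which a sex adjustment would not address. This too stands: bias is not shown and may be zero.

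**Conclusion.** The concern holds. The printed gender statistic and p-value are wrong as the result of the test described, and the sex totals contradict each other. If the group counts are right, the correct result is 5.867 on 3 df, p=0.118 instead of p=0.546: still not significant, but a much weaker statement of balance. If the enrolled 22/22 is right, at least one group count is wrong and the conclusion cannot be stated until the counts are known. The range of 0.020 to 0.351 rests on the assumption of exactly two recodings and carries no probability weighting. The documents do not show which split is right. This should be corrected, but it does not by itself overturn any biomarker finding.

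**What to change.** 1. Check the sex of all 44 participants against source data and correct the opening section, Demographic Findings, or both.
2. Re-run the four-group chi-square on the confirmed counts and replace the printed result, stating df. If the group counts are confirmed, suitable wording is: *Gender did not differ significantly across the four groups (chi-square=5.867, df=3, p=0.118).* If 22/22 is confirmed, report the new value and re-examine the conclusion.
3. Report the confirmed sex split for SP vs P and SH vs H, and state possible confounding of the smoking contrasts by sex as a limitation.
4. Optional, and supportive only: add sex to a linear model of transformed or rank-transformed periostin for SP vs P at days 0 and 15, giving estimates and confidence intervals without new significance claims. It would not resolve the grade difference between SP and P.

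The required part costs one check of 44 entries, one re-run test and a few sentences. Its downside is a less favourable balance statement and, if 22/22 is right, possibly a changed conclusion.

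The optional part is two models and 1 df in each. In the four-group model on the printed counts, the variance of SP vs P rises from 2/11 = 0.1818 to 0.1818 + (4/11)²/9.4545 = 0.1958 (in units of the residual variance), where 9.4545 = 2 × (7×4/11) + 2 × (3×8/11) is the within-group sum of squares of sex. The standard error therefore rises by about 3.8% (0.9% to 9.2% over the ten tables), before any gain from explained variance. Extending this to three biomarkers at three times would mean nine models and a multiplicity problem, so it is not proposed.

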## **Clinical Parameters**

### **Full Mouth Clinical Findings**

When the pre-treatment (day 0) data were evaluated, a significant difference was found between the groups in all clinical parameters (PI, GI, BOP, PD and CAL). The measurements of SP and P groups were higher than the healthy groups ( $p<0.05$ ).

When the results of the in-group treatment were evaluated, the data before the treatment (day 0), the 15th day and the 30th day after the treatment were compared and it was observed that there was a statistically significant decrease in all clinical parameters (PI, GI, BOP, PD, CAL) in both the SP group and the P group.

There was no statistically significant difference between the periodontitis groups (SP-P) and healthy groups (SH-H) on the 0th, 15th and 30th days in terms of smoking ( $p>0.05$ ).

